Despite the 80% - 90% survival rate, there are no effective treatments or interventions for vincristine-induced peripheral neuropathy (VIPN) and one is urgently needed. Our long-term goal is to develop and implement interventions to minimize the persistent effects of VIPN. The proposed study will assess the feasibility of exercise (EX) as a therapeutic intervention for pediatric patients with ALL and LL who have clinically significant VIPN. The EX component will be a mix of aerobic, dynamic resistance and isometric exercises. Emerging data support the notion that **exercise protects against** chemotherapy-induced peripheral neuropathy (CIPN)⁹ and **may help repair damaged nerves** after CIPN develops¹⁰. Specifically, exercise increases many molecular signals, such as nerve growth factor (NGF), growth associated protein 43 (GAP 43) and synapsin (SNAP1), which induce axonal repair in peripheral nerves¹¹. Exercise also decreases levels of serum chemerin¹², a pro-inflammatory protein and genetic marker associated with VIPN in children. The primary objective of this study is to assess the feasibility as well as determine preliminary effect size estimates of EX in preparation for a fully powered efficacy trial. Forty children and AYA (ages 5-25 years) who are on treatment for ALL or LL and exhibit a total neuropathy score of 3 or greater, will be recruited. The impact of EX on the subject's total neuropathy and quality of life, will be measured at baseline (T1) and following the 8-week study (T2). Our study will address the following specific aims:

Aim 1: Evaluate the feasibility and acceptability of EX as an intervention for VIPN in pediatric patients with ALL and LL

Hypothesis 1: Subjects will complete $\geq 50\%$ of the EX sessions during the 8-week intervention.

Hypothesis 2: Children, AYA and parents will report satisfaction with the intervention and its components.

Aim 2: Estimate preliminary effect sizes of the EX intervention.

Hypothesis 1: The EX intervention will lead to improved VIPN (lower TNS-PV scores) at the end of the intervention T2 (14 weeks: primary endpoint) compared to baseline T1 (6 weeks)

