We plan to enroll 40 children and AYA who develop VIPN so that we will have at least 34 children and AYA who will complete the 14 week time point (assuming a 15% attrition rate based on this population). This study is sufficiently powered to detect a .5 SD difference in TNS-PV at the 14 week time point with 80% power based on a paired t-test with type I error set at .05. In a previous study of TPN-VS (Smith et al.) assessments from children with high severity VIPN resulted in TNS-PV of (n = 165 assessments from 14 children, mean = 8.02, SD = 5.22), for middle severity (n = 559 assessments from 70 children, mean = 4.22, SD = 3.01), and for low severity TNS-PV (n = 342 assessments from 25 children, mean = 1.94, SD = 1.86). Based on a pooled SD = 3.17 from these three groups, there is approximately a 1.9 SD difference in mean TNS-PV between the high and low severity groups, a 1.2 SD difference between the high and middle severity groups and a .7 SD difference between the middle and low severity groups. Thus if our children and AYA mimic the middle severity group prior to treatment we should be adequately powered to detect if our intervention is able to move them to low severity. Additionally, in pilot data (unpublished) TNS-PV at baseline (1 month) was 3.36 with SD = 3.66. With 34 children and AYA, we will have 80% power to detect a 2 point change in TNS-PV (which is considered clinically meaningful) assuming a SD = 3.66 at both time points and .4 correlation between time points with a paired t-test with type I error set at .05. For FACES (range 0 to 5), based on Smith et al, we estimate the pooled SD = .7 for high, middle, and low severity groups. With a sample size of 34, we are powered to detect a .35 mean difference in FACES, based on a paired t-test with type I error set at .05.

For other outcomes, which we do not have pilot data, we will still be able to detect a .5 SD difference in the mean based on a two-sided paired t-test with type I error set at .05. Even if we do not detect statistically significant differences in these outcomes in the proposed study, estimated means and SDs can be used for planning larger studies in the future.

H.2 Fitbit tracker justification

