Adherence will be measured by self-report of session completion (See Appendix III) and activity tracking via FitBit. All participants will be asked to fill out a short 5 question survey following their EX session regarding their workout, energy level, food intake, and sleep quality. Parents will be asked to initial and review the questions and add any additional comments they feel would be helpful for us to know. The Daily Log is designed not just to aid the child in planning and goal setting, but also to give parents an opportunity to provide positive reinforcement for the child's daily exercise. The patients will also be asked to hit a start EX button on the FitBit at the beginning of the intervention which shows that they have started the video and then hit it again upon completion. The instructor in the video will prompt the child to start and stop their FitBit as a reminder.

Acceptability

Patient Satisfaction Survey: This satisfaction survey was adapted from an existing exercise intervention satisfaction survey⁹⁰. The satisfaction survey consists of 13 items, and they will be asked to respond to each item using a 5 point scale. Patients will provide feedback on the exercise program, exercise videos and therapist support. There is also an open response question for additional feedback (See Appendix XIV).

Parent Satisfaction Survey: Parents will also be asked to complete a satisfaction survey regarding the exercise program, exercise videos, and therapist support. To assess the satisfaction of the parents/caregivers of pediatric cancer patients (peripheral neuropathy symptoms) while participating in an exercise intervention during the Consolidation Phase of chemotherapy⁹⁰. The satisfaction survey consists of 13 items, and they will be asked to respond to each item using a 5 point scale. (See Appendix XV)

Domain, Measurements and Schedule for Study Outcomes

Domain	Measure	# Items	Schedule	
			T1	T2
Predictors				
Demographics	Gender, age, race/ethnicity, pre-diagnosis exercise level		X	
Medical Characteristics	Neuropathy, Weight, ALL/LL diagnosis		X	
Physical Functioning	Baseline Standardized Fitness Assessment	13	X	
Self-efficacy	SLT Exercise Questionnaire	10	X	
Outcome Expectations	SLT Exercise Questionnaire	10	X	X
Support	SLT Exercise Questionnaire	10	X	X
Primary Outcome				
Feasibility	Percentage of subjects that can complete the 8-week intervention FitBit data Daily Log	6	Weeks 6-13	

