Acceptability	Patient Satisfaction Survey Parent Satisfaction Survey	13 13		X
Secondary Outcomes				
Physical Activity				
Total Activity Time during study	FitBit Tracker Daily Log	8		
Heart Rate	FitBit Tracker	NA	Weeks 6-13	
Exercise	Fitbit Tracker Daily Log	8		
Biomarkers				
Germline DNA Chemerin levels PDGF-BB levels IL-13 levels GAP 43 Synapsin NGF	Blood Draw	NA	X	X

Neuropathy

	NCI CTCAE Version 4.02	2		X
	Total Neuropathy Score - Pediatric Vincristine (TNS-PV)	25	X	X
	Total Neuropathy Score - Clinical (TNSc)	7	X	X

Pain

	P-CIN Pediatric Chemotherapy-Induced Neuropathy Patient Reported Outcome	13	X	X
	Pediatric Neuropathic Pain Scale - Five	6	X	X

Quality of Life

	Peds QL V4 Scale	23	X	X
	Ferrans and Powers	66	X	X

I.5 Blood Sample Collection

This study will include collection of a minimum of 15 mL of whole blood at 2 time points: baseline or pre-intervention (week 6) and post-intervention (week 14). Blood samples will be stored at -80°C until analysis for germline DNA, chemerin levels, NGF, SNAP1, GAP43 and cytokines PDGF-BB and IL-13. Whenever possible, blood will be drawn at the same time as blood is drawn for routine clinical purposes. Blood will always be drawn by trained technicians. Please refer to the Laboratory Manual for this study for blood collection, processing, transfer and storage instructions.

I.6 Data Processing and Storage

Survey Data: All survey study data collected will be stored in the Research Electronic Data Capture (REDCap) database. REDCap is managed through the Department of Biostatistics in the Indiana University School of Medicine. Access to the password-protected database will be limited to study personnel, and any data shared outside of the study team will be de-identified prior to distribution.

Fitbit Data: The Fitbit data will be automatically imported to a Fitbit application on the company's secure server and then uploaded automatically to an excel file. The data will be downloaded weekly to a password protected master excel file folder stored on a university secured server and managed by the Bioinformatics core (See human subjects section for further details). All physiological measures: Heart Rate, Steps, Distance and Activity, will be captured using the Fitbit Charge HR.

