To address Aim 1, adherence in the intervention group will be measured through a 5 question survey at each treatment and also through start/stop on the Fitbit. Adherence scores will be summarized across time with descriptive statistics (N, mean, SD, median, minimum, and maximum). From start/stop information, the proportion of exercise sessions completed and the proportion of patients which complete at least 50% of the exercise sessions along with associated 95% confidence intervals will be estimated. Additionally, descriptive statistics will be provided for the patient satisfaction survey provided at the end of the study.

To address Aim 2, we will use paired t-tests to examine change from baseline (T1) to 14 weeks (T2). For outcomes which are known to be non-normal such as biomarkers, we will use Wilcoxon-signed rank tests. We plan an intent-to-treat analysis. Even if we do not see significant differences, descriptive statistics including means, SD, and effect sizes (differences in means between the two time points divided by pooled SD) will be reported for outcomes along with 95% confidence intervals. All analysis will include checking of assumptions. Additionally, we will also use repeated measures ANOVA to estimate the contrast of interest (change from baseline at 14 weeks) for primary and secondary outcomes, after adjusting for age and baseline activity level.

For activity outcomes obtained from the FitBit, such as patients' daily number of steps, distance, active minutes, and heart rate, we will start with simple techniques such as paired t-tests or Wilcoxon signed-rank tests to compare the mean change in activity level from baseline (T1: summarized over week 6) to treatment end (T2: summarized over week 13). As an exploratory analysis, we will also use a generalized linear mixed model with appropriate distribution (e.g. Poisson) and link function fit to all weekly outcomes to examine changes over time using time as a continuous variable. We expect to have an abundance of information provided from the Fitbit, thus we will estimate descriptive statistics (N, mean, SD, median, minimum, and maximum) for all outcomes (i.e., number of steps, distance, active minutes, and heart rate) at each week to aid in planning future studies.

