
Criteria for removal from the study are as follows:

- The participant expresses significant distress related to completion of the study (the PI will refer the participant to clinical services if needed).
- The participant provides verbal or written notification that s/he has decided to discontinue study participation.

Any other reason for which the principal investigator believes the participant should be withdrawn.

M. PATIENT CONSENT AND PEER JUDGEMENT

The protocol and informed consent form for this study must be approved in writing by the appropriate Institutional Review Board (IRB) prior to any patient being registered on this study.

Changes to the protocol, as well as a change of principal investigator, must also be approved by the Board. Records of the Institutional Review Board review and approval of all documents pertaining to this study must be kept on file by the investigator and are subject to inspection at any time during the study. Periodic status reports must be submitted to the Institutional Review Board at least yearly, as well as notification of completion of the study and a final report within 3 months of study completion or termination.

The study will be conducted in compliance with ICH guidelines and with all applicable federal (including 21 CFR parts 56 & 50), state or local laws.

N. REFERENCES

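### Acceptability is a listed primary outcome, but no satisfaction survey is planned for participants who leave the study before T2, so the reported result is likely to be too favourable

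*Combined protocol and SAP*

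**What the plan says.** Aim 1, Hypothesis 2 (section B) reads: "Children, AYA and parents will report satisfaction with the intervention and its components". It sets no threshold and is not limited to those who finish.

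The table of domains, measures and schedule in section I.4 has two rows under its Primary Outcome heading. Feasibility is measured as "Percentage of subjects that can complete the 8-week intervention FitBit data Daily Log". Acceptability is measured by "Patient Satisfaction Survey Parent Satisfaction Survey", and the only schedule mark for those two instruments is at T2. For each instrument the text of I.4 states: "The satisfaction survey consists of 13 items, and they will be asked to respond to each item using a 5 point scale". It does not define what counts as satisfied.

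Section J.2 provides that "descriptive statistics will be provided for the patient satisfaction survey provided at the end of the study". It gives no denominator and no handling of absent surveys, and it does not mention the parent survey.

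Section L lists three grounds for removal from the study: "The participant expresses significant distress related to completion of the study"; "The participant provides verbal or written notification that s/he has decided to discontinue study participation"; and any other reason the principal investigator considers sufficient. No assessment is attached to any of them.

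Section H.1 states "We plan to enroll 40 children and AYA who develop VIPN", so that at least 34 complete week 14 at an assumed 15% attrition. Section J.3 expects no substantial bias from this attrition and plans one related analysis, a comparison of baseline characteristics between those who complete and those who do not.

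**The concern.** The only acceptability measurement comes after every route out of the study, and one of those routes is distress caused by taking part. A person who leaves on that ground may well rate the programme lower than someone who stays. Neither that person nor the parent has a planned survey, so the group that answers is selected on something probably related to the answer.

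Nothing else in the plan fills the gap. Enrolling extra patients, as J.3 relies on, restores precision but does not undo selection. The baseline comparison in J.3 cannot address satisfaction, which has no baseline value. Intent-to-treat is named for the pre/post design in section H and under Aim 2 in J.2, but neither place says how a leaver's satisfaction would be obtained.

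What is at stake is the accuracy of a descriptive figure. The study's stated purpose is to prepare a fully powered efficacy trial, and how leavers judged the programme is information that trial would use. Once they have left unasked, their answers can only be bounded, not estimated.

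**Working it through.** **Inputs.** From H.1: 40 enrolled, 34 completers, 15% attrition. From I.4: 13 items on a 5-point scale. The documents give no expected satisfaction level, so every satisfaction value below is an assumption. I also assume that the scale is coded 1 to 5, that all attrition is departure from the study before T2, and that every completer returns the survey.

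**The plan's own figure.** 34 / (1 - 0.15) = 40, which agrees with H.1. The number with no planned survey is 40 - 34 = 6, and 6 / 40 = 15%.

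**Mean score.** Let M be the mean among stayers and m the mean among leavers.

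All-enrolled mean = 0.85M + 0.15m, so the respondent mean exceeds it by 0.15 x (M - m).

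- Gap of 1 point: 0.15 x 1 = 0.15.
- Gap of 2 points: 0.15 x 2 = 0.30. For example, M = 4.0 and m = 2.0 give (34 x 4.0 + 6 x 2.0) / 40 = 3.70.
- Gap of 4 points, the largest possible: 0.15 x 4 = 0.60.

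**Proportion satisfied.** Let p be the share among stayers, q the share among leavers and a the attrition.

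All-enrolled share = p(1 - a) + qa, so the overstatement is a(p - q).

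With p = 85% (assumed) and a = 15%:

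| Share of leavers satisfied (assumed) | All-enrolled share | Overstatement |
|---|---|---|
| 0% | 0.7225 + 0 = 72.25% | 12.75 points |
| 50% | 0.7225 + 0.075 = 79.75% | 5.25 points |
| 75% | 0.7225 + 0.1125 = 83.5% | 1.5 points |
| 85% | 0.7225 + 0.1275 = 85% | 0 |

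The ceiling at 15% attrition is 15 points, reached when every stayer and no leaver is satisfied.

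**Bounds that assume nothing about leavers.** With k satisfied among 34 respondents, the share over all enrolled lies between k/40 and (k + 6)/40.

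- k = 31: 31/34 = 91.2% reported; 31/40 = 77.5% to 37/40 = 92.5% over all enrolled.
- k = 34: 100% reported; 34/40 = 85% to 40/40 = 100% over all enrolled.

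The upper bound for k = 31 is above the reported figure, so the arithmetic alone does not fix the direction of the bias.

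**The case against.** **Who is missed.** A reader might infer that any child who gives up the exercises is never asked. The documents do not support that. Section L concerns removal from the study, and nothing in it removes a child who stops using the videos. Such a child is still due the T2 survey. The gap is confined to those who leave the study.

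**Direction.** A reader might also take the upward bias as shown. It is an inference. Only the first ground in section L refers to distress. A voluntary exit, or one at the investigator's discretion, may have nothing to do with the programme. H.1 attributes the 15% to this population without giving reasons, and these are patients in consolidation chemotherapy. Leavers with 75% satisfied would shift the example by only 1.5 points. This objection stands: likely is the right word.

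**Consequence.** Hypothesis 2 has no threshold and J.2 plans only description, so no pass/fail decision can be wrong. This also stands.

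**Signal captured elsewhere.** Poor acceptability will show partly in the completion percentage and in the proportion completing at least 50% of sessions. Post-session questions with parent comments, and prompt reporting to the IRB of withdrawals due to distress, add some information. None of these asks for the ratings of the programme, videos and therapist support that the satisfaction surveys collect. The number of respondents should be visible against 40, so a worst-case bound can be worked out afterwards, but a bound is much less informative than an answer.

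**Unseen forms.** The surveys themselves (Appendices XIV and XV) are in a separate file. Instructions there on use at exit cannot be ruled out, but the protocol's schedule and section L refer to none.

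**Status of the outcome.** Aim 2, Hypothesis 1 and J.3 apply the term primary endpoint to the 14-week time point. That does not alter the table's placing of acceptability under Primary Outcome.

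**Conclusion.** The point holds in limited form. For a listed primary outcome, the plan provides no satisfaction measurement for participants who leave before T2, or for their parents, and no analysis step that acknowledges this. The descriptive result is likely, though not certainly, too favourable.

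At the plan's own 15% attrition, the shift in the mean is 0.15 times the stayer-leaver gap, at most 0.60 on a 1-to-5 scale. A proportion satisfied could be overstated by up to 15 percentage points. With an assumed 85% among stayers, the all-enrolled share runs from about 72% to 85% as the share of leavers satisfied rises from none to 85%. These sizes rest on the assumptions listed in the working and scale with actual attrition.

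The absence of the parent survey from J.2 is a separate drafting gap. It does not bear on the direction of the bias, but it belongs in the same correction because Hypothesis 2 includes parents.

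**What to change.** **Schedule table (I.4) and section L.** Offer the existing Patient and Parent Satisfaction Surveys when a participant leaves the study, as well as at T2. Completion should be optional, in clinic, by phone or by email. Section I.3 already allows phone and email for check-ins.

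**Section J.2.** Summarise both the patient and the parent survey. Report the number of respondents out of all enrolled, and show leavers separately from those surveyed at T2. Add a bound for leavers who do not respond: for a mean, set them to the lowest and then the highest score; for a proportion, count them as not satisfied and then as satisfied. A proportion also needs a stated cut-off, since the plan has none.

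**Cost.** About one line each in the table, section L and J.2, with no new instrument. Some leavers will decline, so the gap will shrink rather than close, and the headline satisfaction figure may be lower. The change has to be in place before participants leave.

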The Fitbit activity tracker was chosen for this feasibility study due to its versatility and effectiveness within younger populations of children. The FitBit's ease of use, comfort, design and feedback features were important factors for all age groups (children and AYA). Researchers in some studies utilized the Fitbit activity tracker to assess adherence to home-based activity programs⁷⁵.

I. PROCEDURES

[figure not shown]
I.1 Overview

For this feasibility study, 40 pediatric patients with a diagnosis of ALL or LL who have a TNS of ≥ 3 at the end of four weeks of vincristine treatment will be enrolled from Riley Hospital for Children, Indiana University Health North Hospital, . Children and AYA will be recruited during their first four weeks after diagnosis and if they have a TNS ≥ 3 at the time of baseline (week 4-6 T1) they will be enrolled into the study. During T1 patients will complete all questionnaires, neuropathy exams, and provide blood samples and then again at week 14 (T2). Neuropathy exam may be performed during weeks 4 through 6 to accommodate regimented clinical visits. Exercise assessments will be performed on week 7. Subjects will check-in with the exercise therapist during weeks 9, 11, and 13 at a minimum, or once a week during the study if they choose (weeks 7-15). These in-

person sessions will take approximately 15 minutes, and the therapist will provide education, evaluate the subject's exercise plan, review exercises, set goals, and make plans to optimize adherence to the exercise program.

All study visits will take place before or after routine clinic visits so that patients and their families do not have to make additional trips to the four hospital sites. EX sessions will be completed by patients at home using instructional videos that will be given to participants during their study orientation.

I.2 Intervention timeline

I.3 Exercise (EX) Intervention

The EX intervention will include both an in-person exercise schedule and at-home video EX sessions (See Appendix I and II). The EX intervention will be designed and led by an AFAA (Athletics and Fitness Association of America) certified physical fitness trainer with fifteen years' experience and a professional with a PhD in an Exercise Science related field.

In-Person Exercise Sessions:

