The first session will be completed at one of the four hospital sites with the EX intervention specialist during the baseline visit. Patients will check-in with their intervention specialist during routine visits to one of the sites or phone on weeks 8, 10, and 12 at a minimum throughout consolidation treatment, or once per week if they choose (weeks 7-15). In-person sessions will last approximately 15 minutes each during which time the therapist will provide *education* on the importance of exercise for VIPN, review the exercises, reassess difficulty level, *set exercise goals* for the following week, and *plan* to reach these goals. Reviewing exercises will demonstrate that the patient has learned exercises through *observational learning* from the therapist and peer models on the exercise videos. In-person sessions will also allow the therapist to provide *reinforcement* for the patient's progress.

If the patient or the study team are unable to meet in person the intervention specialist will contact the patient via their prefer contact method (phone call, email, Skype). These sessions will follow the format of the in-person sessions. Education, assessment of difficulty level, set exercise goals and plan will all be discussed during the remote check-in.

Home Exercise Sessions:

At baseline, participants will have access to the exercise videos via the study website or they will be downloaded to the study tablet, with 3 chapters of EX sessions to be completed at home with video instruction. Patients will be asked to complete home EX sessions 6 times per week for 8 weeks (week 6 through week 13) during the consolidation phase of treatment. A Daily Exercise Log is available to record exercise chapters, fatigue level and time of day exercised (See Appendix III). Patients may choose their rest day each week. Each EX session will last approximately 15 minutes. The at-home videos will have the therapist and three children and AYA who are of similar age to the patients demonstrate the exercises. This design is critical for supporting the *observational learning* component of the intervention. Two videos will be available for the study: one for ages 5 – 10; one for ages 11 – 25.

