Ferrans & Powers Quality of Life Index: Total quality of life will be measured using the Ferrans and Powers Quality of Life Index Version III and is a 66-question index designed to evaluate social, psychological, family, and health satisfaction (See Appendix XI). This assessment is valid for ages 19 and above. Higher scores indicate greater satisfaction in quality of life with an internal Cronbach's alpha of 0.93⁸¹.

Social Learning Theory Questionnaire

Self-Efficacy: There is currently no exercise self-efficacy scale for children and AYA's with cancer. We have adapted the Bartholomew physical activity self-efficacy scale for children and AYA's for use in our study⁸². We have adapted the original self-efficacy scale by adding two questions that are specifically neuropathy related and replaced the term exercise where physical activity had been used. Responses to the questions are limited to Yes/No and not applicable. (See Section 1 Appendix XII).

Support: The support module was taken from a larger validated scale developed by Liang et al (2014) which measures physical activity self-efficacy, enjoyment, and exercise social support for children⁸³. The support section of the questionnaire consists of 10 questions rated on a 5 point scale from None to Very often. The items assess support children and AYA's receive from parents and peers to facilitate exercise. We have adapted the term physical activity to the term exercise for this study (See Section 2 Appendix XII).

Outcome Expectations: We adapted an existing exercise outcomes expectations questionnaire from the adult literature for the purposes of our study. The survey consists of 10 items targeting exercise outcome expectations. Patients are asked to rate each item on a 5 point scale. Items were edited for developmental level/appropriateness⁸⁴. (See Section 3 Appendix XII)

Physiological Parameters

[figure not shown]
Fitbit activity tracker: All patients will be instructed to wear their Fitbit activity trackers every day during waking hours throughout the intervention period. The Fitbit activity tracker (specifically the Charge 2) has a five-day battery life and an “always-on” heart rate tracking system. It is an accelerometer that is worn like a small wristband and records data on movement (steps, HR, distance and activity), total activity minutes, heart rate and total minutes of inactivity including sleep. The data is stored on the device and then can be downloaded wirelessly to a computer⁷⁵.

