Six Minute Walk Test: The Six- minute walk test (6MWT) is used to assess subjects’ functional exercise capacity. This assessment will be conducted by an exercise professional during week 7 (T1) and week 15 (T2) physiological assessments. The 6MWT will be conducted following the American Thoracic Society Guidelines⁸⁸ and our standard operating procedures. Subjects will be asked to walk as far as possible for 6 minutes. They will be assessed on how far of a distance is walked over the course of these six minutes. Subjects will be allowed to slow down, stop and rest as needed. They will be asked to resume walking with they are able. This assessment will be performed at all sites.

Romberg Balance Test: The Romberg Balance is an assessment of the subjects balance and proprioception⁸⁹. The patient will be asked to remove their shoes, stand with their feet together, arms held to their side or crossed in front of their chest. They will be asked to stand quietly with their eyes open and subsequently with their eyes closed. The assessor will maintain close proximity to the subject in case there is a loss of balance. Subjects will then be asked to stand heel to toe with one front directly in front of the other. Similar to the first portion of the test patients will be asked to perform this assessment with eyes open and eyes closed. Subjects will be assessed by counting the second they are able to maintain balance.

The baseline Standardized Fitness Assessment: The fitness assessment will evaluate the general health and physical characteristics of each patient (See Appendix XIII). Specifically, data will be collected regarding height, weight, resting heart rate, blood pressure, body composition (ratio of lean body mass to fat mass), lower back and hamstring flexibility, aerobic fitness and physical strength. All tests will be age appropriate. This information will be used to determine the initial exercise level most appropriate for the subject to begin the intervention study.

Adherence

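### The Fitbit baseline week in J.2 is the first home-exercise week in I.3, so the T1-to-T2 activity contrast, as worded, compares the first and last intervention weeks

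*Combined protocol and SAP*

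**What the plan says.** **Analysis.** J.2 compares Fitbit outcomes by paired t-test or Wilcoxon signed-rank test from "baseline (T1: summarized over week 6) to treatment end (T2: summarized over week 13". It names steps, distance, active minutes and heart rate. An exploratory mixed model and weekly descriptive statistics use the weekly Fitbit data. The contrast serves the activity-time and heart-rate parts of Aim 2 Hypothesis 2 (section B), which predicts higher values at T2 than at T1.

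**Exercise period.** Under I.3, Home Exercise Sessions, patients are to "complete home EX sessions 6 times per week for 8 weeks (week 6 through week 13". The same section says: "At baseline, participants will have access to the exercise videos via the study website". Under I.3, In-Person Exercise Sessions: "The first session will be completed at one of the four hospital sites with the EX intervention specialist during the baseline visit". I.1 says that patients who meet the neuropathy threshold "at the time of baseline (week 4-6 T1) they will be enrolled into the study".

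**Tracker wear.** I.4, Physiological Parameters, tells patients to "wear their Fitbit activity trackers every day during waking hours throughout the intervention period". The outcomes table at the end of I.4 shows weeks 6-13 for Fitbit data and nothing earlier, although its layout is broken in the text available.

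**Text that points to a later start.** I.1 states: "Exercise assessments will be performed on week 7". I.4 puts the T1 six-minute walk test in week 7 and says of the baseline fitness assessment: "This information will be used to determine the initial exercise level most appropriate for the subject to begin the intervention study". The minimum check-ins fall in weeks 9, 11 and 13 in I.1, but in weeks 8, 10 and 12 in I.3.

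**The concern.** A change from baseline needs a baseline measured before the intervention starts. If week 6 is already an exercise week, any gain in activity present in that week is subtracted from the reported change. What remains is the further change during the programme, which is not the T1-to-T2 change that Hypothesis 2 describes.

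An early gain is plausible on the protocol's own account. It cites work in which children wearing a Fitbit took more steps (section E, Self-Monitoring; I.4), and it lists the tracker among its reinforcement tools (section E, Reinforcement).

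Aim 2 exists to supply effect sizes for a later efficacy trial. A Fitbit effect labelled as change from baseline, but measured from exercise week 1, could be carried into that planning as something it is not.

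**Working it through.** **1. Count the weeks.** Weeks 6 to 13 inclusive are 13 - 6 + 1 = 8 weeks, which reproduces I.3's eight. At 6 sessions per week that is 8 x 6 = 48 sessions. The count reaches eight only if week 6 is an exercise week.

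**2. Reading A: J.2 with I.3 as worded.** T1 is exercise week 1 and T2 is exercise week 8. If the first session falls partway through week 6, that week mixes days before and after the start, and only part of the initial rise is missed. If it falls at or before the beginning of week 6, which I.1's week 4-6 baseline window allows, all of the rise up to that week's level is missed. The mixed model and the weekly descriptives have no earlier Fitbit data, so they do not supply a pre-exercise value.

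**3. Reading B: exercise starts after the week-7 assessments.** Week 6 could then be a valid baseline. But weeks 7 to 13 are 13 - 7 + 1 = 7 weeks, or 7 x 6 = 42 sessions. Eight weeks from week 7 run to week 14, so week 13 is not the end of an eight-week programme.

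**4. Compare the readings.** Reading A conflicts with week-7 assessments that are meant to set the starting level. Reading B conflicts with I.3's weeks and with J.2's treatment end. Two other items do not discriminate. I.5's pre-intervention blood draw in week 6 fits A if blood is taken before the first session, and optional check-ins in weeks 7-15 are compatible with either start.

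**5. Reproduce the plan's power figure.** H.1 gives 34 completers, a two-sided paired t-test, alpha .05, and a 0.5 SD difference for outcomes without pilot data. Read in SD-of-change units, the noncentrality is 0.5 x sqrt(34) = 2.92 on 33 df, giving power 0.808 against the stated 80%. H.1's TNS-PV example supports that unit: the SD of change is 3.66 x sqrt(2 x (1 - 0.4)) = 4.01, 2 / 4.01 = 0.50, and power is 0.806.

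**6. Illustrate reading A.** Let f be the share of the effect already present in week 6. The documents give no value for f, so a range is assumed and the SD of change is held fixed. The remaining effect is 0.5 x (1 - f).

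| Assumed share f | Remaining effect (SD of change) | Power, n = 34 |
|---|---|---|
| 0% | 0.500 | 81% |
| 25% | 0.375 | 56% |
| 50% | 0.250 | 29% |
| 75% | 0.125 | 11% |

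**The case against.** The strongest reply is that exercise really begins after the week-7 assessments, so week 6 is a sound baseline. The flow diagram, the I.2 timeline and Appendix I are not visible and may show this. That may be the intent, but the written passages would still disagree on the number of exercise weeks and on the end of treatment. For the same reason, the lack of pre-exercise tracker wear can be asserted only for the visible text.

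A second reply is that J.2 defines its quantity clearly: mean over week 6 against mean over week 13. I.3 also describes gradual progression through exercise levels, so first-to-last-week change is a coherent thing to estimate. This stands. The fault lies in calling week 6 a baseline, not in the contrast being meaningless.

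A third reply is that the power figures prove no harm. This also stands. Every non-zero share is assumed, and 0.5 SD is H.1's detectable difference, not an expected Fitbit effect. H.1 accepts non-significance for such outcomes and values means and SDs for planning. The weekly descriptives will still give on-intervention levels and SDs.

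A reader might infer that the whole initial rise is certainly lost, or that the Fitbit effects are shown to be underestimated. The documents support neither. Week 6 may contain pre-exercise days, and nothing is lost if activity does not rise at the start.

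**Conclusion.** The point holds as a contradiction within the current text, with a conditional consequence. Confidence is high that the passages conflict and moderate that the Fitbit estimates would be attenuated. Followed as worded, J.2 and I.3 produce a first-versus-last intervention-week comparison, which does not test the Fitbit activity and heart-rate parts of Aim 2 Hypothesis 2. If exercise instead starts after week 7, the baseline can stand but the eight-week count and the week-13 endpoint do not.

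The size of any bias cannot be derived from the documents. The fall in power from 81% to between 56% and 11% rests wholly on assumed shares of 25% to 75%.

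It would be wrong to extend this to the main results, because neither the feasibility estimates nor the TNS-PV change uses this contrast. The unsettled start week does touch the session count: 50% of sessions within weeks 6 to 13 is 24 of 48 or 21 of 42. In a single-arm study, even a clean Fitbit baseline would leave exercise mixed with the treatment course. The matter should be fixed, but it concerns secondary outcomes.

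**What to change.** 1. Reconcile the exercise start and end weeks across I.1, I.3, the fitness and walk-test text and outcomes table in I.4, I.5, and J.2. Then define the Fitbit T1 and T2 windows relative to each patient's first exercise session rather than by calendar week.
2. If the reconciled schedule yields Fitbit days before the first session, use those days as T1.
3. If it does not, report week 6 versus week 13 as a within-intervention trend. Do not present it as a change from baseline in support of the Fitbit activity and heart-rate parts of Aim 2 Hypothesis 2.

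Anchoring the windows to the first session does not by itself create pre-exercise data, so step 3 may be the one that applies. The cost is wording only, with no extra devices, visits or patients. The downside is a weaker secondary claim under step 3. No start week is recommended, and no change to the timing of any intervention component is proposed.
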